off painful areas in patients with intermetatarsal bursitis, reducing pain and disability, which was supported by ultrasound findings [15].

The literature has been consistent in pointing out the positive effects of foot orthoses on comfort in the short term. For example, studies such as that of Tarrade et al [16] found significant improvements in the pain of workers who remained standing for long periods of time when using foot orthoses. However, the medium to long term evidence for this is still not very clear. Among the scarce evidence on this subject, García-Hernández et al. [17] demonstrated that manufacturing workers showed greater comfort after a period of adaptation, which occurred between one and two months after starting the use of foot orthoses. Carrying out this process, using modern, tailor-made manufacturing systems could mean better results, as these methods have proven to be the most effective in generating foot orthoses.

Though the shape of people's feet varies from person to person, currently typical shoes have inside standard foot orthoses that do not provide customized designs to fit the differences in shape of the foot of each person who uses them. This generates a wide range of loading and pressure distribution along the sole. This can generate pain and a reduced quality of life in the people who use them. Today we have the possibility of designing foot orthoses tailored to each person's foot, which generates a support and impacts absorption according to the shape of one's foot, which would allow us to generate greater comfort and thus avoid discomfort and injuries caused by the alteration of the loads. The goal of this study is to find out whether the use of software generated custom-made orthopedic foot orthoses improves pain in the long term.

3) Inclusion and Exclusion Criteria

The attending orthopaedic foot and ankle surgeons will identify patients based on clinical exam and/or radiographic findings. Screening and eligibility will be conducted by the research coordinator.

Inclusion Criteria:

1. Foot/ankle pain or pathology OR diagnosed pes planus, pes cavus, pronator foot, supinator foot, metatarsalgia, Morton's neuroma, sesamoiditis, hallux valgus, intermetatarsal bursitis.
2. Between 18 and 65 years of age
3. BMI is greater than 18.5 or less than 30.

Exclusion Criteria:

1. Individuals who have had surgery in the lower limbs during this past year.
2. Individuals who already have custom-made orthopedic orthoses.

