3. Patients with active diabetic ulcers or chronic foot pressure ulcers.

4) Study Timelines

We aim to enroll up to 60 participants over the course of 1-3 months. Each participant will be evaluated at baseline, when the customized foot

PROTOCOL TITLE: Evaluation of Software Generated Customized Foot Orthoses

orthoses will be made, and the corresponding tests will be conducted. Subsequently, consecutive surveys will be carried out at 0, 7, 30, 120, and 360 days. days from the first day of foot orthoses use to measure the change in pain and comfort with use of the foot orthoses. An interim analysis will be conducted after all subjects have completed the 30-day time point. This interim analysis will allow us to determine whether subjects are using the foot orthoses they have been provided. Complete primary analyses is estimated to be completed within 3 months after the termination of the study.

5) Study Endpoints

Primary endpoint: Successful patient use of a 3D printed custom orthotic for at least 6 months and up to 1 year

6) Secondary endpoint: Improvement in patient report outcomes after the use of a 3D printed custom orthoticProcedures Involved

The evaluation will have a duration of approximately 30 minutes, which consists of four stages:

- a. Collection of personal data and anamnesis: The patient's demographic data, anthropometric measurements and anamnesis will be consulted.
- b. Physical examination: Visual and palpitory inspection of the foot.
- c. Baropodometry: Taking of plantar pressures by means of a platform.
 - i. Static: Subjects should remain standing on the platform measuring plantar pressures for 15 seconds with arms at the sides and looking straight ahead. There is only 1 sample.
 - ii. Dynamic:
 1. Walking: Subjects should walk over the pressure measurement platform. Five shots per foot, with a protocol of 5 steps to reach the platform.
- d. Hindfoot photography: A photograph of the hindfoot will be taken, which allows us to measure the angulation of the hindfoot.

Making and Delivery of Foot Orthoses:

During a period of 2 weeks, the foot orthoses will be created using Soleit software which will later be manufactured via three-dimensional printing.

Use of Foot Orthoses:

Foot orthoses will be sent to participants along with a small instruction manual and protocol of use. When using the foot orthoses for the first

PROTOCOL TITLE: Evaluation of Software Generated Customized Foot Orthoses

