I understand that if this study involves use of UC Davis students' educational records (including records in the PI's own possession such as course exams/assignments), I must consult with the Registrar's office to see if all requirements of the Family Educational Rights and Privacy Act (FERPA) are satisfied.

Data Analysis & Statistical Considerations:

PROTOCOL TITLE: Evaluation of Software Generated Customized Foot Orthoses

A quasi-experimental, within-subject (repeated measures) and longitudinal controlled design will be established. Patients will be recruited from the patient population at the University of California, Davis Orthopaedic Foot and Ankle Clinic. From the total number of enrolled subjects who meet the inclusion criteria, an optimal N of 52 subjects will be randomly selected, considering a medium effect size (0.4) and a p less than 0.05 to achieve a statistical power of 0.8. Being a longitudinal study, a sample loss of 10% was established. Therefore, 60 subjects will be included in the study. We aim to enroll up to 60 participants over the course of 1-3 months.

Intra-subject pain, comfort, and quality of life averages pre-use and post use of the foot orthoses will be compared. The sample of participants will be described with central tendency statistics and baseline parameters, and post use evaluations (0, 7, and 30, 120, and 360 days after first foot orthoses use) will be established. These will be compared to study possible differences. For normally distributed dataions, repeated measures, one-way ANOVA for paired samples will be used for normal distributions will be used with a Tukey's post-test and in case of non-normal distributions, Friedman's test will be used with a Dunn's post-test. All analyses will be performed with the SPSS statistical package.

Privacy, Data Storage & Confidentiality:

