4. Protocol Deviations: Failure to follow the protocol due to the action or inaction of the investigator or research staff. Exception – If the protocol deviation was taken in order to eliminate an apparent immediate hazard to a participant, the PI must report the information within 24 hours.

5. Breach of confidentiality: must be reported within 24 hours.

6. Change to protocol taken without prior IRB review to eliminate an apparent immediate hazard to a participant: must be reported within 24 hours.

7. Complaint of a participant that cannot be resolved by the research team.

8. Unanticipated adverse device effect. Exception – if the unexpected and at least probably related adverse device effect results in the death of a research subject, the PI must report the information within 24 hours.

All data collected will remain confidential. Data will be stored securely under the patient’s study identification number. All clinical data, images and surgical/procedural data will be de-identified prior to any in-house or public presentation of data or images. Coded data will only be released to those listed as study investigators or support staff. Paper data records will be stored in locked file cabinets in a locked office. All electronic research data will be stored on the PI computer that is password protected and encrypted.

IRB, FDA and any applicable regulatory agencies will have access to the study records upon request. The data and associated identifiers will be kept for up to 5 years in a locked research facility accessible only to designated personnel, at which time the data will be destroyed per hospital policy. If the results of this study are published, the data will be reported

PROTOCOL TITLE: Evaluation of Software Generated Customized Foot Orthoses

collectively without mention of any subject's identity, thereby ensuring subject anonymity.

10) Withdrawal of Subjects

Subjects may withdraw from the study at any time. Subjects may be withdrawn by an investigator if the participant does not participate in study follow-ups. Research staff will document the reason for withdrawal. Subjects who fail to appear at initial visit or do not receive the foot orthoses will be considered screen failures and will be removed from the study and the study data.

11) Risks to Subjects

Risk Assessment and Device-Related Risks:

Discomfort:

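### Section 10 counts eligible, evaluated subjects who get no device as screen failures and removes them from the study data, so successful use can be reported only among recipients.

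*Protocol*

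**What the plan says.** Section 10 (Withdrawal of Subjects) puts two groups under one rule: those who do not attend the initial visit, and those who "do not receive the foot orthoses will be considered screen failures and will be removed from the study and the study data". The sentence just before it reads "Research staff will document the reason for withdrawal".

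The steps before receipt are set out elsewhere in the protocol:

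- Section 3: "Screening and eligibility will be conducted by the research coordinator". The criteria are diagnosis or pain, age, BMI and three exclusions. Receiving a device is not one of them.
- Section 4: participants are evaluated at baseline, before the device exists. Section 6 lists the content: history, physical examination, plantar pressures and a hindfoot photograph.
- Section 6, in its part on making and delivery, gives the production step: "During a period of 2 weeks, the foot orthoses will be created using Soleit software which will later be manufactured via three-dimensional printing".
- Section 6, in its part on use, gives the dispatch step: "Foot orthoses will be sent to participants along with a small instruction manual and protocol of use".

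Section 5 gives the primary endpoint as "Successful patient use of a 3D printed custom orthotic for at least 6 months and up to 1 year". It states no denominator.

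**The concern.** A screen failure is ordinarily someone found not to meet the entry criteria. Here the label also covers people who met them, completed the baseline evaluation and then got no device. Non-receipt could arise in design, printing or shipping, or because the subject withdrew while waiting. The protocol describes no such events, so these causes are examples only.

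The study is titled an evaluation of software generated orthoses and its declared primary endpoint is successful use. If non-recipients leave the study data, a reader of the results cannot see how often an evaluated patient ended up without a device, or why. Nor can a use rate among all evaluated patients be computed from those data. A statistical analysis plan could choose a denominator, but it could not use subjects whom the protocol has already taken out of the data.

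Section 10 is also unclear within itself. A subject who withdraws between baseline and delivery falls under both the sentence on recording the reason for withdrawal and the sentence on removal, and nothing says which governs.

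**Working it through.** **The plan's own figures.** Section 7 states "an optimal N of 52 subjects will be randomly selected, considering a medium effect size (0.4) and a p less than 0.05", with power 0.8, and raises this to 60 for a 10% loss. A two-sided paired t-test at 0.05 with standardised effect 0.4 needs N = 52 (power 0.808), which matches. Inflating for loss gives 52/0.9 = 57.8, so 58, within 2 of the planned 60. The sample size is not in dispute. It also rests on an effect size for a mean change and not on a use proportion, so the point below does not affect it.

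**Order of events.** Screening (section 3), baseline evaluation (sections 4 and 6), about 2 weeks of design, printing, dispatch and receipt (section 6), first use, follow-up. Failure to attend the initial visit falls before baseline, so calling it a screen failure is unremarkable. Non-receipt falls after both eligibility and baseline.

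**Effect on the use rate.** Let N be the number evaluated, m the number who receive no device and s the number of successful users.

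- Rate available under section 10: s/(N − m)
- Rate among all evaluated, non-receipt counted as not successful: s/N
- Ratio of the first to the second: N/(N − m), which is never below 1

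Inputs: N = 60 from section 7, assuming all 60 are evaluated. The document gives neither m nor s. Assumed values are m = 0 to 12, with success among recipients of about 70% (range 60% to 80%).

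| Not received (m) | Recipients | Ratio | Successes (assumed) | Among recipients | Among all 60 | Gap (points) |
|---|---|---|---|---|---|---|
| 0 | 60 | 1.00 | 42 | 70.0% | 70.0% | 0 |
| 3 | 57 | 60/57 = 1.05 | 40 | 70.2% | 66.7% | 3.5 |
| 6 | 54 | 60/54 = 1.11 | 38 | 70.4% | 63.3% | 7.0 |
| 12 | 48 | 60/48 = 1.25 | 34 | 70.8% | 56.7% | 14.2 |

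Over 3 to 12 non-recipients and 60% to 80% success, the gap runs from 3.0 points (34/57 = 59.6% against 34/60 = 56.7%) to 15.8 points (38/48 = 79.2% against 38/60 = 63.3%).

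**The case against.** The strongest reply is that recipients are a coherent population here. The study has a single arm with within-subject comparisons, so there is no randomised contrast to protect. The stated objectives are pain, comfort and quality of life, not feasibility of manufacture. Follow-up is timed from first use and adverse event collection starts with use, so a non-recipient has no day 0 and no outcome. The endpoint itself can be read as use by a patient who has the device. All of this stands. It supports a recipients-only rate as one reported figure and recipients-only comparisons of pain, comfort and quality of life. It does not support removing the others from the data, which rules out any second figure.

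Four stronger readings are tempting, and the document does not bear them out.

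- *The primary result is biased upward.* That is so only if the target is use among all evaluated subjects. The protocol states no denominator, and choosing that one is a choice, not a correction of an error. Against use among recipients, this rule introduces no bias.
- *The number enrolled can never be reconciled.* Section 7 keeps a separate identification listing, section 9 keeps data and identifiers for up to 5 years, and section 10 asks for withdrawal reasons. Removal from the study data may mean only exclusion from the analysed dataset; no text orders enrolment records destroyed or forbids counting screen failures.
- *People who give up early vanish from the results.* The sentence reaches only those who withdraw before receipt. Someone who receives the device and then does not wear it, or finds it uncomfortable, is not removed by it.
- *Many subjects are affected.* The document gives no non-receipt rate. It also leaves the base of 60 uncertain, since section 7 speaks both of 52 randomly selected from those enrolled and of 60 included, and it does not say whether removed subjects are replaced.

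**Conclusion.** The point holds in a limited form. Section 10 gives the wrong label to a post-eligibility event and takes the subjects concerned out of the study data. What results is a use rate available only among recipients, with non-receipt hidden from the reported results. Relative to all evaluated subjects, the rule can only raise the rate or leave it unchanged. The factor is 60/(60 − non-recipients), assuming 60 evaluated and non-receipt counted as not successful; if every evaluated subject receives a device, the effect is nil. The actual size cannot be known from the document. The sample size and the pain, comfort and quality-of-life comparisons among recipients are not called into question.

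**What to change.** In section 10, limit screen failure to people who do not meet the criteria or never attend the initial visit. Keep every eligible subject who completed the baseline evaluation in the study data, with the number of non-recipients and the reason for each. Say that a subject who withdraws before receipt is handled in the same way.

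Report successful use among all evaluated subjects, with non-receipt counted as not successful, alongside the rate among recipients, and label each clearly. Pain, comfort and quality-of-life comparisons stay on recipients.

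The cost is a reworded sentence and one extra denominator in the report. The downside is a use rate that may look slightly lower. No clinical procedure changes.
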